Appendix 1. Schedule of Events

Procedure /Test	Pre-procedure	Procedure	Post-procedure		Follow-up Visits	
			24 hrs. (+/- 6 hrs.)	Day 5-7 / Discharge (whichever is earlier)	30 Day (+/- 7 days)	90 Day (+/- 14 days)
Patient Informed Consent	x					
Medical history	x					
Neurological Examinations						
NIH Stroke Scale	x		x ²	x	x ³	x
Modified Rankin Scale	x ¹			x	x	x
Imaging Assessments						
CT/CTA	x ⁴		x ²			
CTP	x		x			
Confirmatory DUS		x				
Angiography		x				
ASPECTS	x					
MRI				x		
Other Assessments						
Endovascular Therapy		x				
Concomitant Medications	x	x	x	x	x	x
Concomitant Therapies	x	x	x	x	x	x
Adverse Events		x	x	x	x	x

¹ Modified Rankin will be evaluated for pre-stroke disabilities.

² To determine presence of symptomatic cerebral hemorrhage.

³ NIH Stroke Scale completed if visit is in-office

⁴ CT/CTA at pre-procedure must be of head and neck

CONTROLLED

Appendix 2. Neurological Assessments/Scoring

Alberta stroke program early CT score (ASPECTS) (Pexman et al. 2001)

The Alberta stroke program early CT score (ASPECTS) is a 10-point quantitative topographic CT scan score used in patients with MCA strokes. Segmental assessment of the MCA vascular territory is made, and 1 point is deducted from the initial score of 10 for every region involved:

- caudate
- putamen
- internal capsule
- insular cortex
- M1: "anterior MCA cortex," corresponding to frontal operculum
- M2: "MCA cortex lateral to insular ribbon" corresponding to anterior temporal lobe
- M3: "posterior MCA cortex" corresponding to posterior temporal lobe
- M4: "anterior MCA territory immediately superior to M1"
- M5: "lateral MCA territory immediately superior to M2"
- M6: "posterior MCA territory immediately superior to M3"

Modified Rankin Scale (mRS)(Broderick et al. 2017)

The modified Rankin scale is used to qualify functional outcome in patient who suffer a neurological event. The scale comprises six levels, from 0 to 5, of increasingly severe disability where 0-2 is generally considered a good outcome with individuals assuming complete functional independence. The assessment should be made in a manner free of attribution to the incident stroke or the subject's condition prior to stroke.

- 0: no symptoms/normal
- 1: no significant disability despite symptoms; able to carry out all usual duties and activities
- 2: slight disability; unable to carry out all previous activities, but able to look after own affairs without assistance
- 3: moderate disability; requiring some help, but able to walk without assistance
- 4: moderately severe disability; unable to walk without assistance and unable to attend to own bodily needs without assistance
- 5: severe disability; bedridden, incontinent, and requiring constant nursing care and attention
- 6: dead

Modified TICI Scale (mTICI Scale)(Zaidat et al. 2013)

The modified thrombolysis in cerebral infarction (mTICI) grading is a tool for determining the response of thrombolytic therapy for ischemic stroke. In neurointerventional radiology it is commonly used for assessing patients post endovascular revascularization.

- 0:** No Perfusion - No antegrade flow beyond the point of occlusion
- 1:** Penetration with Minimal Perfusion - The contrast material passes beyond the area of obstruction but fails to opacify the entire cerebral bed distal to the obstruction for the duration of the angiographic run
- 2:** Partial Perfusion - The contrast material passes beyond the obstruction and opacifies the arterial bed distal to the obstruction; However, the rate of entry of contrast into the vessel distal to the obstruction and/or its rate of clearance from the distal bed are perceptibly slower than its entry into and/or clearance from comparable areas not perfused by the previously occluded vessel, e.g., the opposite cerebral artery or the arterial bed proximal to the obstruction
- 2a:** Only partial filling (< 50%) of the entire vascular territory is visualized
- 2b:** Filling of > 50% all the expected vascular territory is visualized, but the filling is slower than normal
- 3:** Complete Perfusion - Antegrade flow into the bed distal to the obstruction occurs as promptly as into the obstruction and clearance of contrast material from the involved bed is as rapid as from an uninvolved other bed of the same vessel or the opposite cerebral artery.

National Institutes of Health Stroke Scale (NIHSS)(Meyer et al. 2009)

The NIHSS is a graded neurological examination assessing consciousness, eye movements, visual fields, motor and sensory impairments, ataxia, speech, cognition and inattention. Often used to assess the severity of strokes based on the 11 components:

1. level of consciousness (1a: 0-3, 1b: 0-2 and 1c: 0-2)
2. best gaze (0-2)
3. visual fields (0-3)
4. facial palsy (0-3)
5. arm motor (0-4)
6. leg motor (0-4)
7. limb ataxia (0-2)
8. sensory (0-2)
9. best language (0-3)
10. dysarthria (0-2)
11. extinction and inattention (0-2)

These 11 components are then summed and the score correlates to stroke severity:

- 0 = no stroke symptoms
- 1-4 = minor stroke
- 5-15 = moderate stroke
- 16-20 = moderate to severe stroke
- 21-42 = severe stroke

Appendix 3. Abbreviations

Abbreviation	Term
ACA	Anterior Cerebral Artery
AE	Adverse Event
AHA	American Heart Association
AIS	Acute Ischemic Stroke
ASA	American Stroke Association
CCA	Common Carotid Artery
CFR	Code of Federal Regulations
CRA	Clinical Research Associate
CRF	Case Report Form
CT	Computerized Tomography
CTA	Computerized Tomography Angiography
CTP	Computerized Tomography Perfusion
CV	Curriculum Vitae
CVA	Cerebral Vascular Accident
DE	Distal Embolization
DNR	Do Not Resuscitate
ECA	External Carotid Artery
ECG	Electrocardiogram
ENT	Embolization to New Territory
EVT	Endovascular Treatment
FDA	Food and Drug Administration
GCP	Good Clinical Practice
HIPAA	Health Insurance Portability and Accountability Act
IA	Intra-Arterial
ICA	Internal Carotid Artery
ICA-T	Internal Carotid Artery-Terminus
ICF	Informed Consent Form
IFU	Instructions for Use
ID	Identification
IM	Intramuscular
Inc.	Incorporated
IRB	Institutional Review Board
ITT	Intent-To-Treat
IU	International Unit

Abbreviation	Term
IV	Intravenous
LAR	Legally Authorized Representative
LVO	Large Vessel Occlusion
MCA	Middle Cerebral Artery
MRA	Magnetic Resonance Angiography
MRI	Magnetic Resonance Imaging
mRS	Modified Rankin Scale
mTICI	Modified Thrombolysis in Cerebral Infarction
N/A	Not Applicable
NIH	National Institutes of Health
NIHSS	National Institutes of Health Stroke Scale
NPS	Neuroprotection System
PHI	Patient Health Information
PP	Per Protocol
SAE	Serious Adverse Event
SADE	Serious Adverse Device Effect
SICH	Symptomatic Intracranial Hemorrhage
TCAR	Transcarotid Artery Revascularization
TIA	Transient Ischemic Attack
TIMI	Thrombolysis in Myocardial Infarction
tPA	Tissue Plasminogen Activator (alteplase)
UADE	Unanticipated Adverse Device Effect

Appendix 4. Definitions

Access Site Complication

Complication related to the vascular access site for the index procedure including but not limited to dissection, pseudoaneurysm, hematoma, arteriovenous fistula, thrombus formation, embolization and any vascular complication that may be attributed to the device AND that requires surgical repair, surgical wound revision, transfusion etc.

Adverse Event (AE)

Any unintended disease or injury or untoward clinical sign in a research patient.

CEA—Carotid Endarterectomy

A surgical procedure in which atherosclerotic plaque is removed from the diseased carotid artery.

CVA—Cerebral Vascular Accident (See definition for Stroke)

Death

Cessation of brain, cardiac, and pulmonary functions

Neurologic Death Death due to stroke or other neurologic cause.

Cardiac Death Death due to MI or other cardiac cause.

Other Death that cannot be attributed to neurologic or cardiac causes.

Device Malfunction

The failure of a device to meet any of its performance specifications or perform as intended. Performance specifications include all claims made in the labeling of the device.

Device Related Adverse Event

An Adverse Event that was directly caused by the study device (NOVIS NPS).

Distal Embolization (DE)

Embolization of pieces of the original thrombus “downstream” in the same vascular territory as the original thrombus.

Embolization to New Territory (ENT)

Any new infarct seen in the ipsilateral ACA for MCA occlusions, on CTA or MRI at the 24-hour time point compared to baseline CT or MRI.

Failed Transfemoral Therapy

Either a transfemoral mechanical thrombectomy attempt was made unsuccessfully with at least 15 minutes having elapsed from groin puncture, or there is inadequate or prohibitive anatomy deeming a transfemoral approach not possible, as determined by the operator.

Good Clinical Outcome

A measure of neurologic functional outcome with a score of 0–2 on the modified Rankin Scale (mRS), assessed at the 90-day follow-up visit.

Intracranial Hemorrhage

A hemorrhage, or bleeding within the skull

Isolated Hemisphere

Intracranial circulation that is fed only by the ipsilateral internal carotid artery and may be detected on prior CTA/MRA

Neurological Deterioration/Worsening

A 4 or more-point increase in NIHSS from baseline to discharge. Neurological worsening could be new or evolution/progression of the index stroke.

Permanent Cranial Nerve Palsy or Injury

Injury to cranial nerves in the vicinity of the treated carotid artery that has not resolved by three months after the intervention. Symptoms will depend on the specific nerve that is injured, such as hoarseness.

Pre-stroke disability

Obtained at baseline, but representative of the patient's status before the index stroke, assessed by mRS on medical history obtained from patient's medical chart, or family members.

Procedure Related Adverse Event

An undesirable event that occurred as a direct cause of the procedure that was not a direct cause of the study device.

Serious Adverse Event (SAE)

An adverse event in a research patient that led to a death, or led to a serious deterioration in the health of the patient that resulted in a life-threatening illness or injury, or resulted in a permanent impairment of a body structure or a body function, or required in-patient hospitalization or prolongation of existing hospitalization, or resulted in medical or surgical intervention to prevent permanent impairment to body structure or a body function. SAEs are a subset of AEs.

Stroke

A neurological deficit lasting 24 hours or more attributed to an acute focal injury of the central nervous system (CNS) by a vascular cause, including cerebral infarction, intracerebral hemorrhage (ICH), and subarachnoid hemorrhage (SAH). Stroke can be subclassified as Hemorrhagic or Ischemic

Symptomatic Intracranial Hemorrhage (SICH)

New intracranial hemorrhage detected by brain imaging associated with any of the items below (Von Kummer et al. 2015):

- ≥ 4 points total NIHSS at the time of diagnosis compared to the pre-procedure NIHSS.
- ≥ 2 point in one NIHSS category. The rationale for this is to capture new hemorrhages that produce new neurological symptoms, making them clearly symptomatic, but not causing worsening in the original stroke territory. For example, a new remote hemorrhage in the contralateral occipital lobe may cause new hemianopia that is clearly symptomatic, but the patient will not have worsening of ≥ 4 points on the NIHSS score.
- Leading to intubation/hemicraniectomy/EVD placement or other major medical/surgical intervention.
- Absence of alternative explanation for deterioration

Technical Success

Successful introduction of endovascular tools through the NOVIS Transcarotid NPS.

Transient Ischemic Attack (TIA)

Temporary focal brain or retinal deficits caused by vascular disease that resolves completely in less than 24 hours.

[figure not shown]
Unanticipated Adverse Device Effect (UADE)

Any serious adverse effect on health or safety or any life-threatening problem or death caused by or associated with a device. The effect must have not been previously identified in nature, severity or degree of incidence in the study plan or IFU. Other unanticipated serious problems associated with the device that relates to the rights, safety or welfare of study patients may also be considered UADEs.

Vascular Access Site Complications

These complications are associated with the NITE procedure whether through the arterial or venous access and are categorized into dissections, hemorrhage, infections, perforations, pseudoaneurysms and ruptures.

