3.2.2 ROADSTER Study

In 2012, Silk Road Medical initiated the ROADSTER study, a multicenter trial of 219 patients to evaluate the safety and effectiveness of the ENROUTE Transcarotid Neuroprotection System (ENROUTE NPS) with all FDA-approved carotid artery stent systems. The ROADSTER study showed a low overall 30-day stroke/death rate of 2.8% and a 30-day stroke rate of 1.4%. It was the lowest reported stroke rate of any multicenter trial of carotid revascularization with independent adjudication. The ROADSTER study supported 510(k) clearance of the ENROUTE NPS in 2015.

The rate of serious arterial dissections (those requiring treatment) in the ROADSTER study was 1.8% (4/219). The rates of arterial dissection deemed to be serious in nature vary across contemporaneous studies of carotid artery stenting and embolic protection devices as shown in Table 1.

Table 1. Rates of Serious Dissection and Hematomas

	ROADSTER	Abbott Acculink (ARChE ^R) P040012¹	Abbott Xact (SECuRITY) P040038	Boston Scientific Wallstent (BEACH) P050019	Covidien Protégé (CREATE) P060001	Cordis Precise (SAPP ^{HIRE}) P030047
Serious Dissection Rate	1.8%	0.0%, 0.72%, 2.07%	3.28%	0.4%	1.2%	Not Reported
Serious Wound/Groin Hematoma	2.3%	Not Reported	Not Reported	2.1%	Not Reported	Not Reported

As these results show, the rate of serious dissection in the ROADSTER study is within the range reported in other pivotal carotid artery stenting and embolic protection device trials (0.0%-3.28%). The rate of serious wound hematoma (defined as non-arterial surgical wound hematomas requiring treatment) was 2.3% (5/219) in the combined population (pivotal and extended enrollment). There were no serious groin hematomas (defined as femoral vein access site hematomas) in the ROADSTER study. Wound/groin hematoma rates are rarely reported in other contemporaneous CAS and EPD studies and thus reports of this event are under-reported in TF-

¹ Rates include ARChE^R 1, 2 and 3 respectively

CAS studies. As a result, direct comparisons against TCAR may not be valid. The BEACH study (Boston Scientific Carotid Wallstent) reported a discreet hematoma rate of 2.1%, and the ROADSTER serious wound hematoma rate is comparable to this rate. The variable definitions and reporting standards for local complications make direct comparisons complex.

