3.2.3 ROADSTER 2 Study

In October 2015, Silk Road Medical initiated the ROADSTER 2 Post-Approval Study, a multicenter study of 692 patients. Results of this study were submitted to FDA on November 25, 2019 via P140026/R013. The primary endpoint was the rate of procedural success at 30 days following the index procedure. Procedural success is defined as acute device success (successful insertion of the ENROUTE NPS and establishment of flow reversal), technical success (deployment of interventional tools) and the absence of a major adverse events (hierarchical stroke/death/myocardial infarction) through 30 days. This study demonstrated a high procedural success rate of 97.9%. High rates of acute device and technical success were demonstrated at 99.7% for both.

The hierarchical major adverse event rate (stroke/death/myocardial infarction) in ROADSTER 2 was 1.7%. The incidence of combined stroke/death was 0.8%. There was one (1) death (0.2%) which was unrelated to both the study device and procedure. That patient expired from a ruptured abdominal aortic aneurysm approximately two weeks following treatment in ROADSTER 2.

There were ten (10) acute cranial nerve injuries reported in the ITT population of ROADSTER 2 (1.4%). Six (6) of ten (10) patients returned for extended follow-up and all cranial nerve injuries had resolved. The resolution of cranial nerve injuries for four (4) patients is unknown, since these patients did not consent to additional follow-up.

There were eight (8) adverse events that were attributed to the study devices (1.3%) including seven (7) arterial dissections (1.1%) and one (1) thrombosed stent (0.2%). The arterial dissection rate in ROADSTER 2 was lower than that of ROADSTER, as ROADSTER 2 used a second-generation device designed to be more atraumatic. In a recent publication comparing TCAR to transfemoral CAS, TCAR was associated with a lower rate of technical failure compared to transfemoral CAS (0.5% vs 1.2%; p<.001)(Schermerhorn et al. 2019).

There were no reports of unanticipated adverse device effects in ROADSTER 2.

TCAR with reverse flow has proven to be a safe and effective treatment for carotid revascularization. With over 20,000 procedures performed worldwide, physician utilization of TCAR has started to evolve into other therapeutic areas for the benefits of the access and the protective aspects of reverse flow.

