12.5 Relatedness

The relationship between the use of the medical device (including the medical - surgical procedure) and the occurrence of each adverse event shall be assessed and categorized by the site Investigator. During causality assessment activity, clinical judgement shall be used, and the protocol consulted. The presence of confounding factors, such as concomitant medication/treatment, the natural history of the underlying disease, other concurrent illness or risk factors shall also be considered by the Investigator. Causality assessment will also be reviewed and adjudicated by the Clinical Events Committee.

Each AE will be classified according to four different levels of causality. The Sponsor and the Investigators will use the following definitions to assess the relationship of the adverse event to the investigational medical device or procedures:

- **Not Related:** The adverse event is determined to be solely caused by the underlying disease, disorder or condition of the study patient, or attributable solely to other extraneous causes (unrelated to the device, device malfunction or procedure).
- **Possible:** the relationship with the use of the investigational device is weak but cannot be ruled out completely. Alternative causes are also possible (e.g., an underlying or concurrent illness/ clinical condition or/and an effect of another device, drug or treatment). Cases where relatedness cannot be assessed, or no information has been obtained should also be classified as possible.
- **Probable:** the relationship with the use of the investigational device seems relevant and/or the event cannot be reasonably explained by another cause, but additional information may be obtained.
- **Causal / Related:** The adverse event is clearly caused by the use of the device, device malfunction or the procedure, as confirmed by: the event is recognized as a known event associated with the device or procedure, the event has a temporal relationship to device or procedure, the event involves the body site or organ the device or procedure is applied to or has an effect on, or event is related error in use.

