8.2.1.1. Summary of Device-Related Serious Adverse Events

All summaries of device-related SAEs will be presented separately and for the individual events.

The number and percentage of patients experiencing device-related SAEs will be summarized. Summary Table 6.6.1 entitled *Summary of Site-Reported Device-Related Serious Adverse Events* will include counts and percentages of patients (and event counts) following the category listed below. Results will be supported by the data presented in Listing 6.6 *Serious Adverse Events*, sorted by patient number and the date of procedure.

- vascular complications including dissection
- pseudoaneurysm
- hematoma
- arteriovenous fistula
- thrombus formation
- embolization
- any vascular complication that may be attributed to the device AND requires surgical repair, surgical wound revision, or transfusion

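### Appendix 4 and section 12.5 disagree on whether a purely surgical complication is device-related, so it is undetermined whether serious cutdown-only events count in the first primary safety outcome

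*Protocol*

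**What the plan says.** Protocol 7.1 has two primary safety outcomes. The first is headed as device-related SAEs and lists vascular complications, hematoma among them. Its attribution wording is loose (possible attribution to the device is enough), and wound revision and transfusion are among the qualifying interventions. The second covers only permanent cranial nerve injury, new symptomatic hemorrhage and dissection from ancillary devices.

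Three other places in the protocol bear on attribution:

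- Appendix 4 defines a device-related event as "An Adverse Event that was directly caused by the study device (NOVIS NPS", and a procedure-related event as "An undesirable event that occurred as a direct cause of the procedure that was not a direct cause of the study device".
- Section 12.5 has the investigator assess the relationship between "the use of the medical device (including the medical - surgical procedure) and the occurrence of each adverse event".
- Section 12 lists device-relatedness and procedure-relatedness as two separate four-level fields on the adverse event form. The only definitions of the levels are those in 12.5.

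The CEC adjudicates relationship to device or procedure (Protocol 13.2). SAP 8.2.1.1 says "The number and percentage of patients experiencing device-related SAEs will be summarized", in a table titled as site-reported. It gives no definition of device-related and no relatedness level. SAP 5 then compares this incidence numerically with device-related SAEs from the ENROUTE program.

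**The concern.** The open neck cutdown is part of every NOVIS procedure, and Protocol 23.4 lists hematoma, dissection and vessel rupture among the risks of surgical transcarotid access. A feasibility and safety study of this route should have a settled rule for such events. Here the rule changes with the passage applied. A serious event caused only by the cutdown is outside the device-related class in Appendix 4, inside the related category in 12.5, and arguably inside under the endpoint's own wording. If it is left out of the first outcome, the second does not catch it.

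At stake are the numerator of a primary safety rate and its comparison with ENROUTE, in a study planned for 30 to 40 per-protocol patients.

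**Working it through.** **Reading the passages together.** Take a serious neck-wound hematoma that needs revision and is caused solely by the cutdown.

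1. Appendix 4: it was not directly caused by the NOVIS system, so it is procedure-related and not device-related.
2. Section 12.5, bottom level: an event is Not Related only if it is due to the underlying disease or is "attributable solely to other extraneous causes (unrelated to the device, device malfunction or procedure". This event is related to the procedure, so it cannot be scored Not Related.
3. Section 12.5, top level: "The adverse event is clearly caused by the use of the device, device malfunction or the procedure". The event meets this. The two middle levels mention only the investigational device, so 12.5 is not consistent within itself.
4. Section 12: the device and procedure fields are separate, but they borrow the merged level definitions from 12.5.
5. Protocol 7.1: hematoma and wound revision are both named, under a looser attribution standard than Appendix 4.
6. No passage says which rule prevails, which relatedness level is the cut, or whether site or CEC attribution governs.

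**Events not affected.** Permanent cranial nerve injury is in the second outcome whatever its attribution. An event directly caused by both device and procedure is still device-related under Appendix 4.

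**Illustration of size.** Inputs are from Protocol 3.2.2: serious dissections 4/219, and "The rate of serious wound hematoma (defined as non-arterial surgical wound hematomas requiring treatment) was 2.3% (5/219").

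- Reproducing the stated rates: 4/219 = 1.83% and 5/219 = 2.28%, as given.
- Assumptions: ROADSTER rates carry over to NITE 1; all 4 dissections are device-related; all 5 hematomas are purely procedural; no patient had both.
- Appendix 4 reading: 4/219 = 1.8%.
- Section 12.5 reading: (4 + 5)/219 = 9/219 = 4.1%, a ratio of 9/4 = 2.25.
- Expected events are n × p. The chance of at least one is 1 − (1 − p)^n.

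| n | Expected at 4/219 | Expected at 9/219 | P(≥1) at 4/219 | P(≥1) at 9/219 |
|---|---|---|---|---|
| 30 | 0.55 | 1.23 | 42% | 72% |
| 40 | 0.73 | 1.64 | 52% | 81% |
| 60 (ITT maximum) | 1.10 | 2.47 | 67% | 92% |

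One reclassified event moves the observed rate by 1/30 = 3.3 points, 1/40 = 2.5 points or 1/60 = 1.7 points.

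**Range.** The documents do not say how ROADSTER attributed these nine events. If all nine were device-related, the two readings agree at 4.1%. If all nine were purely procedural, the readings give 0% and 4.1%. The 1.8% figure lies between these extremes. Section 3.2.2 also reports a lower rate of serious access-site complications, 0.7%, among its secondary endpoints. Putting 0.7% in place of 2.28% gives 1.83% + 0.7% = 2.53% for the wider reading, and 1 − (1 − 0.0253)^30 = 54% at n = 30. That substitution may mix two ROADSTER populations.

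**The case against.** The best defense is that the plan means to keep device and procedure apart. Section 12 has two fields, the CEC looks at both, and 12.5 is a general causality scale rather than the endpoint definition. The endpoint itself names hematoma, wound revision and transfusion. No hypothesis is tested (Protocol 14.3), the comparisons are numerical only, and every serious event still appears in SAP Table 6.6 and Listing 6.6. Most of this stands, and it limits the point. It does not settle which rule defines the numerator, because the separate fields have no separate level definitions and the SAP names neither a rule nor a source beyond a site-reported table title.

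Three stronger readings are tempting and are not supported:

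- A reader might infer that Appendix 4 removes any event to which the procedure contributed. It removes only events that the device did not directly cause.
- A reader might infer that a wound hematoma is definitely outside both primary safety outcomes. Given the wording of Protocol 7.1, its inclusion is unclear; exclusion is not established.
- A reader might infer that ENROUTE used the narrow rule, because ROADSTER 2 reports "eight (8) adverse events that were attributed to the study devices (1.3%) including seven (7) arterial dissections" and one thrombosed stent. That list covers adverse events, not only serious ones. The section gives no wound-hematoma count, and the SAP names PROOF and ROADSTER as the comparator studies. The list does not show how wound hematomas were attributed.

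**Conclusion.** The concern holds in a limited form. For serious vascular or wound events caused purely by the cutdown, the documents do not determine whether they enter the first primary safety outcome, and such events would not fall under the second. Alpha and power are not involved. The effect is on a descriptive primary rate in which a single event is worth 3.3 points at n = 30.

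The contrast of 1.8% with 4.1% shows how large the effect could be under assumed attributions and elective TCAR rates. It is not a forecast for NITE 1, nor a documented reclassification of ROADSTER events. Whether the ENROUTE comparison is like for like cannot be judged, because the comparator's attribution rule is not given.

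**What to change.** - In Protocol 12.5, define the device and procedure scales separately at all four levels, to match the two fields in section 12 and the two classes in Appendix 4.
- In Protocol 7.1 and SAP 5 and 8.2.1.1, state one attribution rule for device-related, the relatedness level that counts, and whether site or CEC attribution governs.
- In SAP Table 6.6.1, add a row for serious vascular or access-site events that are device- or procedure-related, beside the device-related row. The primary outcome need not be replaced.
- In the ENROUTE comparison, use the same rule on both sides where the ENROUTE data allow. Otherwise compare all serious access-site events regardless of attribution.

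Deleting the exclusion clause from the Appendix 4 procedure definition would not be enough. It would widen the procedure class and leave the device-related numerator unchanged.

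The cost is wording in both documents through the usual amendment route, one table row, and a check of what the ENROUTE data recorded. Both NITE 1 relatedness fields are already collected. The stated safety rate may look less favorable.
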